performed with the binary weight loss endpoint. This analysis will include a best-case scenario (assuming subjects with missing values have all lost over 5% body weight), a worst-case scenario (assuming no subjects with missing values have lost over 5% body weight), and a tipping point analysis (as described in Yan¹). We will check the assumption that the data is missing completely at random, and use multiple imputation techniques to reduce bias in the estimation of the treatment effect. Missing data will be clearly reported and included in tables.

Power Calculation

The primary outcomes are TBWL from the start of treatment until the 12-month mark and the number of subjects who lose at least 5% of their baseline total body weight. We will power both of these tests at the 0.025 significance level (a Bonferroni correction to maintain a family-wise error rate of 0.05 in our primary analysis). For TBWL, we will test the following null and alternative hypothesis:

$$\begin{aligned} H_0: \mu_t - \mu_c &\leq 5\% \\ H_1: \mu_t - \mu_c &> 5\% \end{aligned}$$

where μ_t and μ_c are the treatment and control mean TBWL in the ITT population. We will use a one-sided two-sample t-test to determine if there is a statistically significant difference in TBWL between our control and treatment arms beyond a superiority margin of 5%. With a total sample size of 90 subjects (30 sham and 60 active treatment), this t-test will have 80% power at the $\alpha = 0.025$ significance level to detect an effect size of $d = 0.63$. Assuming a similar standard deviation of TBWL as the ReShape trial (7.5%), this translates to a detectable difference in TBWL between the treatment and control groups of 4.75%. Assuming this same standard deviation, a two-sample superiority test will have 80% power assuming that the true difference between groups is 6.33%.

For the proportion of treatment subjects who lose at least 5% of their baseline total body weight, we will test the following null and alternative hypothesis:

$$\begin{aligned} H_0: P_t &\leq 35\% \\ H_1: P_t &> 35\% \end{aligned}$$

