where P_t is the proportion of treatment subjects who lose at least 5% of their body weight by the twelve month follow-up. With a total sample size of $n = 60$ active treatment subjects, an exact binomial test will have 80% power at the 0.025 significance level to detect an effect size of $h = 0.321$. This effect size is equivalent to observing a response rate of 50.8% in the treatment group, similar to that seen in the ReShape study. We note that our pilot data indicated that all subjects reached this endpoint, but the sample size was too small to reliably estimate an effect size for the use of powering this study (Kramer 2006).

Anticipating a drop out rate of 15%, we will plan to recruit $n = 106$ total subjects overall in the study across both sites.

Interim Analysis

No interim analysis will be performed.

Representativeness Analysis

As per the guidance from the FDA relating to the representativeness of the study population (<https://www.fda.gov/downloads/MedicalDevices/DeviceRegulationandGuidance/GuidanceDocuments/UC>

M507278.pdf?source=govdelivery&utm_medium=email&utm_source=govdelivery) the following analyses will be conducted:

For each demographic characteristic an appropriate statistical test will be conducted to flag any differences between the two respective subgroups (active and sham device). For categorical data either a Chi-square test (if $n \geq 5$ in each table cell) or Fisher's exact test (if $n < 5$ in any single table cell), will be used, and for continuous a 2-sample t-test will be used to compare the respective subgroups.

References

Yan, Lee & Li (2009). Missing Data Handling Methods in Medical Device Clinical Trials. *Journal of Biopharmaceutical Statistics*, 19: 6, 1085-1098.

Food and Drug Administration. Summary of Safety and Effectiveness Data (SSED) for ReShape Integrated Dual Baloon System. 2015.

Pre-enrollment Screening

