17. POTENTIAL BENEFITS

The current study will contribute to the field of knowledge about the neurological mechanisms that control body mass composition. We will also determine whether the relatively inexpensive, and non-invasive technique of VeNS is an effective treatment for obesity and fat loss. This is of particular importance given the current obesity pandemic and the serious public health challenge that this poses.

A potential benefit for participants is that they may experience some degree of weight loss as a result of participation. This is true for both the experimental and control groups, as both will be receive weight loss counseling from the ACTRI's dietician, Ms [name], as well as receive one year's access to the GB Healthwatch 360 app. This app will assist them in making healthy dietary decisions, and exercises they can undertake, in order to reduce their weight.

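### The 5%-margin weight-loss test has about 12% power, not 80%, at a true difference of 6.33%, and the two primary power statements are not tied to one planning scenario

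*Combined protocol and SAP*

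**What the plan says.** Section 9, Statistical Considerations, Power Calculation, sizes two primary outcomes, both derived from 12-month percent total body weight loss (TBWL). On alpha: "We will power both of these tests at the 0.025 significance level", a Bonferroni split of 0.05.

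- **Mean TBWL.** The null is a difference of at most 5%. "We will use a one-sided two-sample t-test to determine if there is a statistically significant difference in TBWL" between the arms "beyond a superiority margin of 5"%. The sample is given as "With a total sample size of 90 subjects (30 sham and 60 active treatment"), with d = 0.63 detectable at 80% power. The SD is borrowed: "Assuming a similar standard deviation of TBWL as the ReShape trial (7.5"%), which turns d into 4.75%. The paragraph ends by saying that "a two-sample superiority test will have 80% power assuming that the true difference between groups is 6.33"%.
- **Responders.** The null is an active-arm rate of at most 35%, tested by an exact binomial test in 60 subjects, with h = 0.321 claimed to be detectable at 80% power. On the rate behind that figure, the plan says: "This effect size is equivalent to observing a response rate of 50.8% in the treatment group, similar to that seen in the ReShape study".

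Neither arm's mean TBWL is stated, and no distribution or sham response rate is assumed. Section 17 says participants may lose some weight, adding "This is true for both the experimental and control groups". Appendix 2 gives both arms the same dietitian sessions and app.

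**The concern.** The 4.75% figure is the distance from the null that 60 versus 30 can detect. When the null sits at 5%, that distance must be added to the margin. A true difference of 6.33% lies only 1.33 points beyond the margin, so 80% power there looks impossible with the stated SD and sample size.

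There is a second problem behind it. Response is a cut of the same variable as mean TBWL, so an assumed response rate and SD imply an arm mean. The plan never makes that link. A reader therefore cannot tell what power the TBWL test has under the effect used to size the responder test. If it is very low, half the alpha is spent on a test with little prospect of success, and a failed TBWL result could be read as evidence against the device when the planning figures already made failure likely.

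**Working it through.** **Inputs (Power Calculation):** 60 active, 30 sham, SD 7.5%, margin 5%, one-sided 0.025, active response 50.8%, binomial null 35%. **Added assumptions:** equal SD in both arms, and a normal distribution unless stated.

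**1. Reproduce the plan's detectable effect.** SE = 7.5 × √(1/60 + 1/30) = 1.677, with 88 df. The noncentral t gives 80% power at d = 0.633, and 0.633 × 7.5 = 4.75%. This matches the plan, for distance from the null.

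**2. Check 6.33% against the 5% margin.** Noncentrality = (6.33 − 5)/1.677 = 0.793; the critical t is 1.987; power = 12.0%. Other readings of the test do not give 80% either:

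| Reading at 6.33% | Power |
|---|---|
| Margin 5, one-sided 0.025 | 12.0% |
| Margin 5, two-sided 0.025 | 7.2% |
| Margin 5, one-sided 0.05 | 19.5% |
| Margin 0, one-sided 0.025 | 96.2% |

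The difference that gives 80% is 5 + 4.75 = 9.75%. To have 80% power at 6.33% would take about 375 sham and 750 active subjects, or an SD of about 1.33/0.634 = 2.1%.

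**3. Check the responder statement.** With n = 60 and null 0.35, rejecting at ≥28 has size 0.041, above 0.025. Rejecting at ≥29 has size 0.0228. Exact power at 50.8% with ≥29/60 is 69.5%, not 80%. The printed h = 0.321 equals (1.645 + 0.842)/√60, the arcsine approximation at one-sided 0.05.

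**4. Put both primaries on one scale.** If 50.8% lose at least 5%, the active mean is 5 + 7.5 × Φ⁻¹(0.508) = 5 + 7.5 × 0.0201 = 5.15%.

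| Sham assumption | Difference | Chance that the margin test rejects |
|---|---|---|
| Mean loss 0% (25.2% responders) | 5.15% | 3.1% |
| Half the active response, 25.4% (mean loss 0.04%) | 5.12% | 2.9% |
| Mean loss 0.15% | 5.00% | 2.5% (null boundary) |
| Mean loss 1% | 4.15% | 0.7% (null true) |
| Mean loss 2% | 3.15% | 0.1% (null true) |

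**5. Run it the other way.** With sham at 0%, an active mean of 9.75% implies Φ((9.75 − 5)/7.5) = 73.7% responders. An active mean of 6.33% implies 57.0% responders, with 93.2% exact binomial power.

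**6. Sensitivity to shape.** With right-skewed (Pearson III) distributions of SD 7.5% in both arms and 50.8% versus 25.4% responders, skewness from 0.5 to 2 gives differences of 5.2% to 5.4% and power of 3% to 4%. The sham-at-0% row is less stable. At skewness 1 the active mean for 50.8% responders is 6.37%, so the noncentrality is (6.37 − 5)/1.677 = 0.82 and power is about 12%.

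**The case against.** The strongest reply is that each printed effect is the smallest one detectable by its own test. Such figures need not describe one population, and 50.8% is a floor for the responder test, not a ceiling on the active mean. This stands. A larger device effect satisfies both: active 6.33% with sham 0%, or active 8.33% with sham 2% (67.1% responders, 99.9% binomial power). At a true difference of 10% the margin test has 84% power.

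A reader might therefore go too far in three ways:

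- **That the two statements are incompatible, or that 6.33% requires the sham arm to gain weight.** With 50.8% responders, a 6.33% difference puts the sham mean at 5.15 − 6.33 = −1.18% (a gain) under normality. At right skewness 1 it is +0.04%, and at 2 it is a loss of 1.1%. The documents state no distribution, so this depends on the model.
- **That the sponsor expects 50.8%.** The text only likens it to the reference trial. It also says that all pilot subjects responded, while setting that aside as too small a sample for powering.
- **That the TBWL test must fail whatever the device does.** The 3% holds only with active response fixed at 50.8%.

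The sham rows are also assumptions. Primary Outcome Measures asks for approximately double the sham proportion, but no sham rate is planned, and Section 17 says only that weight loss may occur.

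None of this touches step 2, which uses the plan's own inputs for that test.

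**Conclusion.** The 80% claim at 6.33% is wrong. Power against the 5% margin is about 12%, and 80% needs about 9.75%. This rests only on the printed SD, sample size, alpha and margin.

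The link between the two primaries is a conditional finding. At 50.8%, the one active response rate the plan ties to outside experience, the margin test has about 3% power if sham subjects respond at half the active rate (3% to 4% under right skew), or if sham loses 0% on average under normality. It has less if sham subjects lose weight on the shared program. Conversely, a 9.75% difference with sham at 0% corresponds to about 74% responders. Correcting 6.33% to 9.75% alone would thus still leave the section without one stated scenario for both tests. The missing joint scenario is a gap in the plan; it is not a proven contradiction.

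**What to change.** In the Power Calculation:

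1. Delete the statement of 80% power at 6.33%. Replace it with about 12% power at 6.33%, or 80% power at about 9.75%, against the 5% margin with SD 7.5%, 60 versus 30, one-sided 0.025.
2. State one planning scenario: active mean, sham mean, SD, assumed distribution, and the response rates these imply in each arm.
3. Report the power of both primary tests at that scenario. If 50.8% is kept, give the exact binomial power as 69.5% (reject at ≥29/60).
4. Show a short range of sham mean losses, since both arms receive the lifestyle program.

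The cost is a few lines of text and recalculation, with no extra patients and no need for outcome data. The downside is a much less favourable stated power for TBWL. The rewrite makes that power visible but does not raise it.

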Methods: Primary Aims

For total body weight loss (TBWL) as a continuous measure, we will use a two-sample t-test to examine the differences between the control and active treatment groups at each time period. We will also build one-sided confidence intervals to test whether the difference between groups exceeds a superiority margin of 5%. As a secondary analysis, we will also use a linear regression with TBWL as the dependent variable and group and other covariates of interest (gender, age, etc.) as independent variables. To assess any longitudinal effects, we will use a linear mixed effects model for weight over time, with fixed covariates for baseline weight, time, group, and a time / group interaction, and a random intercept to account for within-subject correlation. We will use a one-sided exact binomial test to determine if the response rate in the treatment group significantly exceeds 35%, with response defined by a loss of at least 5% of their body weight at the 12-month follow-up. We will also use Fisher's exact test to compare the response rates in each group, and, as a secondary analysis, will consider the use of a logistic regression to control for any other covariates of interest. To investigate possible longitudinal trends, we will fit a logistic mixed effects model, similar to the linear mixed effects model described above.

Methods: Secondary Aims

For each continuous and categorical variable at each time point, we will use a two-sample t-test and Fisher's exact test, respectively. Summary statistics (mean, standard deviation, quantiles, counts, and percentages) and plots will be produced for all demographic and study outcomes. We will investigate the effectiveness of the device by usage by including usage time as a continuous covariate in a linear model for TBWL. CTRI Biostatistics Core personnel will conduct all analyses using the latest version of R (R Foundation for Statistical Computing, Vienna, Austria. <http://www.R-project.org/>). No alpha spending function is applied to adjust for multiple comparisons across the secondary aims, and no claims will be made based on any of the secondary endpoints, which are instead viewed as hypothesis generating endpoints.

Missing Data

The primary hypotheses will be tested on the intent-to-treat population. A sensitivity analysis will be

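### The responder test (50.8% against 35%, 60 active subjects) has about 70% power at the stated 0.025, not 80%; the 80% matches a calculation at one-sided 0.05

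*Combined protocol and SAP*

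**What the plan says.** All of the relevant text is in section 9, Statistical Considerations.

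- **Level.** Power Calculation names two primary outcomes, mean total body weight loss (TBWL) and the 5% responder outcome, and says: "We will power both of these tests at the 0.025 significance level". The reason given is "a Bonferroni correction to maintain a family-wise error rate of 0.05 in our primary analysis".
- **Test.** Methods: Primary Aims specifies a one-sided exact binomial test in the active arm, asking "if the response rate in the treatment group significantly exceeds 35" percent. Power Calculation repeats the hypotheses as a null of at most 35% against more than 35%.
- **Power claim.** For 60 active subjects, "an exact binomial test will have 80% power at the 0.025 significance level to detect an effect size of" h = 0.321. The plan then turns h into a rate: "This effect size is equivalent to observing a response rate of 50.8% in the treatment group, similar to that seen in the ReShape study".
- **Sample size.** The 60 active and 30 control subjects are the numbers meant to remain after 15% dropout from 106 recruited (Study Design and Power Calculation).

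**The concern.** The claim fixes the sample size, null rate, alternative, level and sidedness, so the power can be computed without outside information. The stated h looks too small for 80% power at 0.025 with 60 subjects, and it equals to three decimals the value that belongs to one-sided 0.05.

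Type I error is not at stake, because the test and its level stay as written. What is at stake is a stated design property of a primary hypothesis. The 50.8% is the plan's own planning value, tied to an earlier device trial, and section 6 says that the data are meant to support regulatory submissions. A reader who relies on the statement would think the risk of missing that rate is 20%.

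**Working it through.** **Inputs, all from Statistical Considerations.** n = 60 active subjects; null rate p0 = 0.35; alternative p1 = 0.508; h = 0.321; one-sided level 0.025; stated power 80%.

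**1. Do h and the rate agree?** h = 2·arcsin(√0.508) − 2·arcsin(√0.35) = 1.5868 − 1.2661 = 0.3207. They agree within rounding.

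**2. Reproducing the plan's figure.** The arcsine normal approximation gives a detectable h of (z for alpha + z for power)/√n, with √60 = 7.746.

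| One-sided level | Detectable h at 80% power | Corresponding rate | Power at h = 0.321 |
|---|---|---|---|
| 0.05 | (1.645 + 0.842)/7.746 = 0.3210 | 50.8% | Φ(2.486 − 1.645) = 80.0% |
| 0.025 | (1.960 + 0.842)/7.746 = 0.362 | 52.8% | Φ(2.486 − 1.960) = 70.1% |

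The 0.05 row reproduces h, the rate, the sample size and the power together. The 0.025 row does not. With the unrounded h = 0.3207, power at 0.025 is 70.0%.

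**3. The exact test that the plan names.** Reject at the smallest r for which P(X ≥ r | 60, 0.35) does not exceed the level.

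| Reject at | Size at 35% | Power at 50.8% |
|---|---|---|
| 28/60 | 0.0412 | 77.9% |
| 29/60 | 0.0228 | 69.5% |
| 30/60 | 0.0119 | 60.0% |

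At 0.025 the threshold is 29/60 (48.3%) and power is 69.5%. At 0.05 the threshold is 28/60 and power is 77.9%. So the 80% matches the arcsine approximation at 0.05, and an exact calculation gives it at neither level. With the 29/60 threshold, power reaches 80% at a true rate of 52.9%, which is h = 0.363.

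**4. Other approximations at one-sided 0.025.** Normal with null variance 71.8%; the same with continuity correction 67.3%; Wald 68.7%. Reading 0.025 as two-sided lowers power further: 59.7% by arcsine, and 60.0% exact with 0.0125 in the upper tail. No variant gives 80%.

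**5. The other primary calculation, for contrast.** For TBWL, a one-sided two-sample t-test with 30 and 60 subjects and d = 0.63 has 79.6% power at 0.025, and 80% needs d = 0.633. At 0.05 the detectable d would be 0.560. That statement was therefore made at 0.025; the mismatch in level is confined to the responder test.

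**6. More subjects under intention to treat.** Two-thirds of 106 is 70.67, so 70 or 71 active subjects would be randomised.

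| Active n | Reject at | Size | Power at 50.8% |
|---|---|---|---|
| 70 | 33 | 0.0241 | 76.8% |
| 71 | 34 | 0.0171 | 72.9% |

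Power is lower at 71 only because the threshold moves up by one and the actual size falls.

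**7. Sample size for 80% power at 50.8% and 0.025.** Arcsine: (2.802/0.321)² = 76.2, so 77 active subjects. The exact test first reaches 80% at 80 subjects (reject at 37, power 82.3%), dips just below at 81 and 83, and stays at or above 80% from 84 (checked up to 139).

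**The case against.** Five points can be made for the plan.

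- **The cause is inferred.** The documents do not show how the figure was obtained. That is true. The match at one-sided 0.05 is close enough to make it the likely origin, but the shortfall at 0.025 does not depend on it.
- **The analysis is by intention to treat.** The primary hypotheses are tested in that population and multiple imputation is planned, so more than 60 active subjects may count. This stands in part: power could be 73% to 77%. Those figures assume that subjects with missing weights respond at the same 50.8% and contribute full information, which is optimistic. They still miss 80%, and the plan ties its claim to 60.
- **Section 10 speaks of enrolling 150.** Section 9 gives 106 recruited and up to 150 screened, so the 150 is probably a screening number. The two sections should be reconciled, but the claim for 60 subjects is unaffected.
- **It is only a planning statement.** The test, level, endpoint and population do not change, and the detectable rate moves by about 2 percentage points. This is fair, and it is why the repair is cheap. The statement still concerns a primary hypothesis and contradicts the plan's own level.
- **This test is not the whole responder criterion.** The primary outcome also asks for a significant difference between groups, tested by Fisher's exact test. That is correct, so the power given here, corrected or not, is not the chance of meeting the full criterion.

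**Conclusion.** The concern holds. With 60 active subjects, a null of 35% and one-sided 0.025, power at a true rate of 50.8% is 69.5% by the exact test and 70.0% by the arcsine approximation, about 10 points below the stated 80%. The chance of missing that rate is 30.5% rather than 20%. Power of 80% needs a true rate of 52.9%. The shortfall rests only on figures in the plan; that 0.05 was used in place of 0.025 is a strong inference. Describing the 80% as the power of an exact binomial test is inaccurate as well, since the exact test gives 77.9% even at 0.05. The conclusion survives the most favourable intention-to-treat count (76.8% with 70 subjects).

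**What to change.** Replace the responder power statement with wording such as: *With 60 active subjects, the one-sided exact binomial test at 0.025 rejects at 29 or more responders (actual size 0.0228). It has 69.5% power if the true response rate is 50.8% and 80% power if it is 52.9% (h = 0.363).* If the approximation is kept, give h = 0.362 and call it an arcsine approximation. The cost is a text change and a stated power about 10 points less favourable; the test, its level and the data collected stay the same.

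If the sponsor wants 80% power at 50.8%, that is a sample-size decision: at least 80 evaluable active subjects, or 84 to stay clear of the dips from discreteness. At 2:1 allocation and 15% dropout, 80 active means 120 evaluable in all and 120/0.85 = 141.2, so about 142 recruited instead of 106. The progress report shows 24 enrolled and no interim analysis is planned, so either choice can be made without outcome data.

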Data will be transferred in an encrypted PDF format. Trial staff will be given direction on how to share the trial data and given access to one specific section of a controlled cloud service which is controlled via role based access. Once they have authenticated with the service and the service verifies that they have the correct role to access the system they will be directed to a single webpage within the application where they will be able to upload the encrypted PDF. This PDF is generated on the fly and is therefore not stored in another location that could become compromised. Generating the PDF on the fly means that the source data is extracted from the database, processed and delivered in the context of a single request. This is an important factor as this means that after the request finishes the data in the PDF will not be held in application memory once the request is finished and the data relating to the request is freed. After the PDF is generated it is delivered to the assigned statistician using TLS 1.2 (a strong protocol), ECDHE_ECDSA with X25519 (a strong key exchange), and AES_128_GCM (a strong cipher). These data will be transferred for each subject when they complete participation in the study. If they complete the study protocol this will be at the one-year mark, however, if they drop out early then data accrued up until that point will be sent.

References

STATISTICAL CONSIDERATIONS

These statistical considerations were constructed in conjunction with [name] of the bio-statistics unit at the ACTRI.

Randomization

Treatment assignments will be generated via a randomized block procedure, with block sizes randomly chosen in the set {2, 4, 6, 8, 10, 12}. Subjects will be assigned 2:1 between treatment and control groups. Stratification will be performed by gender and center.

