11. RECRUITMENT AND PROCEDURES PREPARATORY TO RESEARCH

The study will recruit subjects via Research Match (see: <https://actri.ucsd.edu/clinical/Pages/using-ResearchMatch.aspx>). Research match is a "is a NIH-sponsored national registry of volunteers who have indicated a willingness to learn more about research studies." The aim of this registry is to connect "researchers with appropriate potential subjects." A proposed recruitment message for use on Research Match is being submitted with this Research Plan for IRB review. Best practice in the management of bias in recruitment will be followed.

In order to improve recruitment numbers we also plan to post the flyer included for review with this submission up at the ACTRI and in authorized locations on the UCSD campus.

We also intend to post an advertisement to Facebook groups relating to weight loss that operate in the Southern California area; if necessary we may ask Facebook to promote this statement via a paid advertisement. The proposed Facebook statement is also included for approval.

We also plan to suggest to active subjects, via phone or email, that they give our contact details to friends or family that may be suitable to participate. In return they will receive \$25 compensation if someone they referred is then enrolled. The proposed text is included with this submission.

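### The representativeness analysis only compares the two randomized arms, so it describes baseline balance and cannot show whether the sample represents the intended population

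*Combined protocol and SAP*

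**What the plan says.** In Section 9, Statistical Considerations, the subsection Representativeness Analysis states its purpose: "As per the guidance from the FDA relating to the representativeness of the study population". It then lists the analysis. Each demographic characteristic is tested "to flag any differences between the two respective subgroups (active and sham device"). The methods are: "For categorical data either a Chi-square test" when every cell holds at least five subjects, with Fisher's exact test otherwise; and "for continuous a 2-sample t-test will be used to compare the respective subgroups". No alpha, list of characteristics or reference population is given.

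Under Randomization in the same section: "Subjects will be assigned 2:1 between treatment and control groups" and "Stratification will be performed by gender and center".

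Four other places bear on the point:
- Methods: Secondary Aims (Section 9) commits to summary statistics and plots for all demographic variables.
- Section 10 says nobody is excluded for race, socioeconomic status, language or ethnicity.
- Section 11 promises good practice on recruitment bias, with no analysis attached.
- Section 12 says that data on people ruled out at telephone pre-screening are destroyed once the call ends.

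**The concern.** Representativeness asks whether the people enrolled resemble the people for whom the device is intended. Answering that takes a comparison between the enrolled sample and something outside it. The planned tests compare two randomized parts of the same sample, so the analysis does not address the question it is named for.

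The question matters in this trial. Section 6 says the data are meant to support regulatory submissions, primarily in the United States. Section 11 recruits through a volunteer registry, campus flyers, paid referrals from active subjects and social media ("We also intend to post an advertisement to Facebook groups relating to weight loss"), and Section 10 requires a smart phone. Section 9 plans 106 subjects with 60 at UCSD, which leaves 106 − 60 = 46 (46/106 = 43%) for a second site, likely in Belfast. A regulator may ask how such a sample relates to intended users. As planned, a clean set of arm comparisons could be read as evidence that it does, and a chance flag as evidence that it does not. Neither reading would be sound.

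**Working it through.** The subsection gives no sample size, power or alpha of its own, so there is no stated figure to reproduce. The check is whether the planned tests respond to an unrepresentative sample.

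**Inputs from the documents.** 60 active and 30 sham evaluable subjects (Section 9, Power Calculation); chi-square, Fisher's exact and t-tests as described in the subsection; randomized assignment.

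**Assumptions not in the documents.** Two-sided alpha 0.05; age SD 12 years; a 50% reference share for the external comparison; simple rather than stratified randomization; 3 to 8 characteristics, treated as independent.

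**Step 1: reasoning.** Let the enrolled pool have share p of some trait. Randomization gives both arms expected share p, so the expected difference is p − p = 0 whatever p is. The null hypothesis of the arm comparison is true for a representative pool and for a badly skewed one, and the rejection rate is the test's size in both cases.

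**Step 2: simulated flag rate of the planned tests, 60 versus 30.**

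| Enrolled pool | Flagged |
|---|---|
| Binary trait, share 50% | 4.6% |
| Binary trait, share 70% | 4.8% |
| Binary trait, share 90% | 3.9% |
| Mean age 45 | 5.1% |
| Mean age 55 | 5.0% |
| Mean age 65 | 4.9% |

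The binary rows use 10,000 simulated trials each and the age rows 20,000. The Monte Carlo standard error near 5% is √(0.05 × 0.95 / 10,000) = 0.2 points for the former and √(0.05 × 0.95 / 20,000) = 0.15 points for the latter, so 5.1% is indistinguishable from 5%. The rate does not rise as the pool shifts.

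**Step 3: chance flags.** With k independent characteristics, P(at least one flag) = 1 − 0.95^k.
- k = 3: 1 − 0.857 = 14%
- k = 4: 1 − 0.815 = 19%
- k = 8: 1 − 0.663 = 34%

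Gender is a stratification factor, so its flag rate should fall below 5% and the totals drop where it is included.

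**Step 4: contrast with an external comparison.** An exact binomial test of the pooled sample against an assumed 50% reference share flags as follows.

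| True enrolled share | n = 90 | n = 106 |
|---|---|---|
| 50% | 4.5% | 4.1% |
| 70% | 97.3% | 98.7% |
| 90% | >99.9% | >99.9% |

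This only illustrates that a pooled comparison responds to skew. The documents give no reference distribution, so no trial-specific figure can be computed.

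**The case against.** The strongest reply has four parts.

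**The arm comparison is not worthless.** Randomization balances arms in expectation only. Stratification covers gender and center, so age, race/ethnicity and BMI can differ by chance between 60 and 30 subjects, and a table by arm describes that. This stands: the comparison is useful as a description of baseline balance. It still says nothing about representativeness.

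**The plan does report demographics.** The summaries promised under Methods: Secondary Aims are most of the raw material needed, and a reader could set them against any population. The open eligibility in Section 10, the recruitment-bias statement in Section 11 and the second site also bear on the matter. This stands in part. A reader might infer that the plan yields nothing on generalizability, but that is true only of the arm tests. What is missing is a named reference, pooled estimates with intervals and a correct label.

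**The cited guidance may itself ask for an arm comparison.** That cannot be checked from the documents. A reader might infer that the plan departs from the guidance, and nothing here supports that. The mismatch is between the subsection's stated purpose and its own method.

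**Nothing hangs on a flag.** No endpoint, claim or decision rule uses these tests, and misreading a chance flag is a possibility rather than a planned step. This stands and keeps the point minor. The 34% figure also needs eight independent characteristics; with four, such as age, sex, race/ethnicity and BMI, it is 19% before allowing for stratification by gender.

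**Conclusion.** The point holds as a minor one. The planned tests cannot detect an unrepresentative sample: their flag rate stays at or below nominal (about 5% per characteristic if alpha is 0.05) whatever the skew. No other section compares the enrolled subjects with an outside population. Any flag under correct randomization is chance, with a probability of at least one of roughly 14% to 34% for 3 to 8 independent characteristics, and less where gender is one of them. The first conclusion rests only on randomization from a single pool; the percentages also rest on the assumed alpha, number of characteristics and independence.

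Primary efficacy inference is unaffected. A reader might also infer that the sample is in fact unrepresentative. The documents do not show that; they show only that the plan has no analysis that could tell.

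**What to change.** 1. Relabel the active-versus-sham comparison as descriptive baseline balance.
2. Under Representativeness Analysis, name a reference source for the intended-use population and say why it was chosen.
3. Tabulate the pooled enrolled sample against that source on age, sex, BMI and, where recorded, race/ethnicity, as means or proportions with 95% confidence intervals, overall and by site. The demographic summaries already planned supply the data.
4. If screened-but-not-enrolled people are compared with those enrolled, limit this to people who attended in person and say so, because Section 12 has data on phone-ineligible people destroyed.

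Treatment effects by subgroup answer a different question and are not needed here.

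The cost is SAP wording, one or two tables, and the work of choosing and defending a reference source. Precision will be modest: for a 70% share, the normal-approximation half-width is 1.96 × √(0.7 × 0.3 / 106) = 8.7 points overall, 1.96 × √(0.7 × 0.3 / 60) = 11.6 points at UCSD, and 1.96 × √(0.7 × 0.3 / 46) = 13.2 points at the second site. The site rows should therefore be read as descriptive.
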